8.3 Vital Signs

Vital signs will include systolic and diastolic blood pressure, temperature, pulse, and respiratory rate.

Absolute and change from baseline values in vital signs measurements will be summarized descriptively by visit, and timepoint. A summary table of subjects with PCS values at any post baseline visit will be presented by visit.

Potentially clinically significant vital signs values (as defined in [Table 13](#)) will be listed by parameters.

Table 13: PCS Values for Vital Signs

Parameter (Unit)	PCS Range
Systolic Blood Pressure (mmHg)	<= 90, >= 140
Diastolic Blood Pressure (mmHg)	<= 60, >= 90
Pulse Rate (beats/min)	<= 50, >= 100
Temperature (°C)	<= 36, > 38
Respiratory Rate (breaths/min)	<= 12, >= 20

Data listings will identify if values are “abnormal, clinically significant” or “abnormal, not clinically significant” and an indication of whether the value meets the PCS criterion.

8.4 Physical Examination Findings

The physical examination will include a general review of the following body systems: general appearance, HEENT, neck / thyroid, respiratory, cardiovascular, gastrointestinal, genitourinary, neurological, musculoskeletal / extremities, skin and other. Physical examination results, with abnormal and clinically significant abnormal findings flagged will be listed.

8.5 12-Lead ECG Analysis

12- Lead safety ECG results will be summarized descriptively by visit and timepoint and change from baseline will be presented. Data listings will identify if values are “abnormal, clinically significant” or “abnormal, not clinically significant”.

Outliers with respect to QTcF will also be tabulated for the following categories:

Absolute value > 450 msec and \leq 480 msec

Absolute value > 480 msec and \leq 500 msec

Absolute value > 500 msec

Increase from baseline \geq 30 msec and < 60 msec

Increase from baseline \geq 60 msec

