7. SELECTION, DISCONTINUATION, AND WITHDRAWAL OF SUBJECTS

7.1. Subject Inclusion Criteria

Subjects must meet the following inclusion criteria:

1. Willing and able to provide written informed consent.
2. Males and females 18 to 65 years of age, inclusive.
3. A female subject must meet one of the following criteria:
 - a. If of childbearing potential – agrees to use a highly effective, preferably user-independent method of contraception (failure rate of <1% per year when used consistently and correctly) for at least 30 days prior to screening and agrees to remain on a highly effective method until 205 days after last dose of study medication. Examples of highly-effective methods of contraception are located in [Appendix 1](#).
 - b. If a female of non-childbearing potential – should be surgically sterile (i.e., has undergone complete hysterectomy, bilateral oophorectomy, or tubal ligation/occlusion) or in a menopausal state (at least 1 year without menses), as confirmed by follicle-stimulating hormone (FSH) levels (≥ 40 mIU/mL).
4. A woman of childbearing potential must have a negative highly sensitive serum pregnancy test (β -human chorionic gonadotropin) at screening and a negative urine pregnancy test on Day -1 before the first dose of study drug.
5. A male subject that engages in sexual activity that has the risk of pregnancy must agree to use a double barrier method (e.g., condom and spermicide) and agree to not donate sperm during the study and until at least 205 days after the last dose of the study medication.
6. Good health and without signs or symptoms of current illness.
7. Normal clinical examination, including:
 - a. No physical examination findings that an Investigator determines would interfere with interpretation of study results.
 - b. Screening ECG without clinically significant abnormalities (see [Appendix 2](#)).
 - c. Creatinine clearance (CrCL) ≥ 80 mL/min as calculated using the Cockcroft-Gault equation:
$$CrCL = \frac{(140 - age) \times (weight \text{ in kg})}{72 \times (serum \text{ creatinine in mg/dL})} \times (0.85 \text{ if female})$$
8. Body mass index (BMI; weight in kg divided by height in m squared) between 18.0 and 32.0 kg/m², inclusive.
9. Willing to refrain from strenuous physical activity that could cause muscle aches or injury, including contact sports, at any time from screening through 30 days after any dose of study drug.

10. Subject has adequate venous access for blood collection.

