APPENDIX 2. ECG AND VITAL SIGN ABNORMALITIES

Important abnormalities from the ECG readings are summarized below:

Abnormality	ECG Parameter			
	HR	PR	QRS	QTcF
Abnormalities on actual values				
Abnormally low	<45 bpm	NA	-	-
Abnormally high	≥120 bpm	>220 msec	≥120 msec	-
Borderline prolonged QT (males)	-	-	-	450 msec to ≤480 msec
Borderline prolonged QT (females)				470 msec to ≤480 msec
Prolonged QT	-	-	-	481 msec to ≤500 msec
Pathologically prolonged QT	-	-	-	>500 msec
Abnormalities on changes from baseline				
Normal QTcF change	-	-	-	<30 msec
Borderline QTcF change	-	-	-	30 msec to ≤60 msec
Abnormally high QTcF change	-	-	-	>60 msec

Abbreviations: bpm = beats per minute; HR = heart rate; NA = not applicable; PR = PR interval; QRS = QRS interval; QTcF = QT interval corrected for heart rate using Fridericia's formula.

Important abnormalities for vital signs are summarized below:

Abnormality	Vital Signs Parameter		
	HR	DBP	SBP
Abnormally low	≤45 bpm	≤50 mmHg	≤90 mmHg
Grade 1 or mild	-	>90 mmHg to <100 mmHg	>140 mmHg to <160 mmHg
Grade 2 or moderate	-	≥100 mmHg to <110 mmHg	≥160 mmHg to <180 mmHg
Grade 3 or severe	-	≥110 mmHg	≥180 mmHg
Abnormally high	≥120 bpm	-	-

Abbreviations: DBP = diastolic blood pressure; HR = heart rate; SBP = systolic blood pressure.

	Grade 1	Grade 2	Grade 3	Grade 4
Fever ^a	38.0 to <38.6°C (100.4 to <101.5°F)	≥38.6 to <39.3°C (≥101.5 to <102.7°F)	≥39.3 to <40.0°C (≥102.7 to <104.0°F)	≥40.0°C (≥104.0°F)

a. Non-axillary temperatures only.

For tachypnea and hypoxia, refer to the grading scale in [Table 9](#).

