Values for continuous laboratory parameters (hematology, chemistry, urinalysis, and coagulation) will be summarized by visit and for the change from baseline using descriptive statistics. The number and percentage of subjects with at least one post baseline PCS value and value that is PCS, for each scheduled post baseline of each laboratory parameter will also be presented. Serology, alcohol/drug screen, and pregnancy test results will be presented in separate listings.

Data listings will include out-of-range flags (L, H) and whether the abnormal values are clinically significant or not and an indication of whether the value meets the PCS criterion.

PCS values for laboratory parameters (as defined in [Table 8](#), [Table 9](#), [Table 10](#), [Table 11](#), [Table 12](#) below) will be listed by category. Normal reference ranges are presented in [APPENDIX D](#).

Table 8: PCS Values for Hematology

Laboratory Parameter (Unit)	PCS Range
Absolute basophils, cells/uL	> 400
Absolute eosinophils, cells/uL	> 800
Absolute lymphocytes, cells/uL	< 600
Absolute monocytes, cells/uL	< 10, > 2100
Absolute neutrophils, cells/uL	< or = 799, > 9000
Erythrocytes, (million/uL)	Male: < 3.8, > 6.4 Female: < 3.3, > 5.5

Laboratory Parameter (Unit)	PCS Range
Hematocrit, %	<20.0,>60.0
Hemoglobin, g/dL	Male: < 10 Female: < 9.5
Leukocytes, (thousands/uL)	< 2.0. > 25.0
Platelet count, thousands/uL	< 100,> 700

Table 9: PCS Values for Serum Chemistry

Laboratory Parameter ,Unit	PCS Range
Alanine aminotransferase, U/L	>or= 1.25 x ULN
Albumin, g/dL	<3.0,>6.0
Alkaline phosphatase, U/L	>or= 2.5 x ULN
Asparate Aminotransferase, U/L	>or= 1.25 x ULN
Amylase, U/L	>or= 1.5 x ULN
Bilirubin total, mg/dL	>or= 1.1 x ULN
Blood urea nitrogen, mg/dL	> 70
Calcium, mg/dL	<7.8,>or= 12.4
Carbon dioxide, mmol/L	<16,>40
Chloride, mmol/L	<65,> 130
Creatinine, mg/dL	> or = 1.1 x ULN
Creatinine Clearance, Estimated, mL/min	< 90
Glucose, nonfasting, mg/dL	<54,>160
Lipase, U/L	> or= 1.5 x ULN
Phosphorus, mg/dL	<2
Potassium, mmol/L	<3,>or=6
Protein total, g/dL	<3.0,>9.0
Sodium, mmol/L	<130,>or=150

Table 10 PCS Values for Lipids

Laboratory Parameter , Unit	PCS Range
Triglycerides, mg/dl	> 500
Low Density Lipoprotein (LDL), mg/dl	> or = 190
Cholesterol, Total, mg/dl	> = or 300

Table 11 PCS Values for Coagulation

Laboratory Parameter , Unit	PCS Range
Activated partial thromboplastin time, seconds	> or = 1.66 x ULN
Prothrombin, International normalized ratio (INR), Ratio	> or = 1.5 x ULN

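### QTcF outlier bands are defined three ways in the protocol, SAP and table shell, one shell row overlaps another, and the SAP vital-sign limits differ from protocol Appendix 2 without explanation

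*SAP*

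**What the plan says.** Protocol Appendix 2 introduces its ECG table with "Important abnormalities from the ECG readings are summarized below". The lowest QTcF band is "450 msec to ≤480 msec" for men and "470 msec to ≤480 msec" for women, followed by "481 msec to ≤500 msec" and above 500 msec. A change below 30 msec is called normal, 30 to 60 inclusive borderline, and above 60 abnormally high. The same appendix gives vital-sign limits.

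The protocol uses Appendix 2 in two places. Inclusion criterion 7b (Section 7.1) requires a "Screening ECG without clinically significant abnormalities" and refers to it. The footnotes to the schedules of events (Tables 1 to 3) cite it for deciding whether outpatient vital signs are abnormal enough to prompt a drug and alcohol screen. Section 12.3 promises incidences of potentially clinically significant (PCS) ECG and vital-sign values but sets no limits.

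SAP Section 8.5 says "Outliers with respect to QTcF will also be tabulated for the following categories" and lists its own bands. SAP Section 8.3, Table 13, lists PCS limits for vital signs. Shell T5.4 (Table 14.3.4.2) gives the rows to be programmed for QTcF. The shells for PCS vital signs (Table 14.3.3.2) and PCS laboratory values restrict the denominator to subjects whose baseline was not PCS and who have a post-baseline assessment.

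**The concern.** Vital signs and ECGs belong to the primary safety endpoint, and ECG parameters are also an exploratory cardiac endpoint. The QTcF shell is the specification for a reported table, yet it contradicts the SAP section it implements, so a programmer cannot follow both. A reader who takes the shell rows as exclusive, which is how SAP 8.5 defines them, would misread the counts.

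The difference between the SAP limits and Appendix 2 is a separate matter. The study report would give PCS incidences under limits that differ from the protocol's only list of ECG and vital-sign limits, with no statement that this was intended. With 8 CD388 subjects per dose and route, moving one subject in or out of a numerator or denominator visibly changes a percentage.

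**Working it through.** The plan gives no figure to reproduce. The check sets the rules side by side and classifies whole-number values under each.

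**QTcF (msec)**

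| | Appendix 2 | SAP 8.5 | Shell T5.4 |
|---|---|---|---|
| Lowest band | 450 to ≤480 men; 470 to ≤480 women | >450 to ≤480, both sexes | >450 to ≤480, both sexes |
| Second band | 481 to ≤500 | >480 to ≤500 | >450 to ≤500 |
| Top band | >500 | >500 | >500 |
| Middle change band | 30 to ≤60 | ≥30 to <60 | >30 to ≤60 |
| Top change band | >60 | ≥60 | >60 |

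*Absolute values, SAP against Appendix 2.* The SAP flags women at 451-469 msec, which is 469 − 451 + 1 = 19 whole-msec values, and Appendix 2 does not list them. For men the only difference is at exactly 450, where Appendix 2 lists the value and the SAP does not.

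*Absolute values in the shell.* On a given day let a, b and c be the numbers of subjects whose maximum QTcF is 451-480, 481-500 and above 500.

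- Row 1 = a, row 2 = a + b, row 3 = c.
- Sum of rows = 2a + b + c, against a + b + c subjects, so everyone at 451-480 is counted twice.
- Row 2 − row 1 = b, so the 481-500 count can be recovered, but only by subtraction.
- The same second row appears in both day blocks of the shell.

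*Changes at the boundaries.*

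| Change | Appendix 2 | SAP 8.5 | Shell T5.4 |
|---|---|---|---|
| 30 msec | borderline | middle band | not counted |
| 60 msec | borderline | top band | middle band |

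Changes of 29, 31, 59 and 61 msec are classed alike in all three.

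**Vital signs**

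| | Appendix 2 | SAP Table 13 | Flagged by the SAP only |
|---|---|---|---|
| Pulse (bpm) | ≤45, ≥120 | ≤50, ≥100 | 46-50 and 100-119 |
| DBP (mmHg) | ≤50, >90 | ≤60, ≥90 | 51-60 and 90 |
| SBP (mmHg) | ≤90, >140 | ≤90, ≥140 | 140 only |

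No pulse, DBP or SBP value is flagged by Appendix 2 but not by the SAP.

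**Scale.** Each CD388 dose-by-route group has 1 sentinel + 7 main = 8 subjects, so one subject is 1/8 = 12.5%. If one subject is PCS at baseline and leaves the denominator, one event becomes 1/7 = 14.3%.

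As an illustration only, take single DBP readings as normal, with assumed means of 70-75 and SDs of 8-10 mmHg (not from the documents). With mean 70 and SD 8:

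- SAP rate = Φ((60.5 − 70)/8) + 1 − Φ((89.5 − 70)/8) = 0.125.
- Appendix 2 rate = Φ((50.5 − 70)/8) + 1 − Φ((90.5 − 70)/8) = 0.013.

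Over the assumed range the SAP limits flag 7-20% of readings and Appendix 2 flags 1-7%. The same calculation for pulse (mean 65-70, SD 8-10) gives 1-7% against 0.1-3%. For female QTcF (mean 410-420, SD 15-20) it gives 0.4-6% against 0-0.7%.

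**The case against.** The best defence is that Appendix 2 is not named as the analysis standard. It serves the entry ECG and the trigger for a drug and alcohol screen, and Section 12.3 leaves the PCS limits open. A SAP may choose more sensitive screening limits, the same limits apply to CD388 and placebo, and the listings carry the investigator's own judgement of clinical significance. The non-PCS-baseline rule has a sensible purpose, which is to keep habitual borderline values out of the percentages. The tables are descriptive, and nothing ties them to escalation or to the study halt.

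All of this stands, and it limits the point. It does not answer the conflict between SAP 8.5 and its own shell, which exists whatever status Appendix 2 has. Nor does it explain why the vital-sign and QTcF limits differ. The SAP's version 3.0 log says PCS ranges were aligned with the study laboratory and protocol parameters. That entry may have been meant for laboratory values only, so the point does not rest on it, but it gives a reader no reason to expect a difference.

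A reader might also infer that subjects who are normal by the protocol are being called abnormal. The documents do not support that in general. Apart from the change below 30 msec, Appendix 2 lists important abnormalities and does not declare all other values normal, and PCS is a screening label.

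**Conclusion.** The second absolute row of shell T5.4 is wrong as written, and the QTcF change boundaries in the SAP and shell are incompatible at exactly 30 and 60 msec. Both should be corrected. The SAP also departs from Appendix 2, without explanation, for women's QTcF at 451-469 msec, pulse at 46-50 and 100-119, DBP at 51-60 and 90, and SBP at exactly 140. Through the baseline restriction, the vital-sign limits also change which subjects are counted in cells of 8. The effect is on descriptive safety incidences only; no error rate is involved.

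Four stronger readings are not supported:

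- The shell does not hide how many subjects exceeded 480 msec. Row 2 minus row 1, plus the row above 500, gives that number.
- It cannot be said that PCS counts would be dominated by values outside Appendix 2. The rates above depend on assumed distributions.
- The SAP's respiratory-rate limits do not conflict with Appendix 2, which has no numerical limit for that parameter.
- The creatinine-clearance limit of 90 mL/min matches the laboratory range in SAP Appendix D. Clearance is scheduled only at screening and as clinically indicated, so few subjects would enter that row.

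**What to change.** 1. In both blocks of shell T5.4 (Table 14.3.4.2), change the second absolute row to above 480 and up to 500 msec, as in SAP 8.5.
2. Use one set of QTcF change-band boundaries in SAP 8.5 and the shell, so that exactly 30 and exactly 60 msec each have one place.
3. Reconcile SAP 8.3 Table 13 and SAP 8.5, including the sex-specific QTcF limit, with protocol Appendix 2. Otherwise state in the SAP and in table footnotes that the limits deliberately differ, and why. Which limits are clinically appropriate is for the sponsor to settle.

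The cost is edits to SAP and shell text and reprogramming of the affected tables and the PCS flags in the listing. No new data are needed. If the sponsor moves to the Appendix 2 limits, fewer borderline values will be flagged, but they remain in the listings.

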8.6 Reactogenicity/Injection Site Inspection

Reactogenicity/Injection Site Inspection will be summarized descriptively, by injection route (IM or SQ), CD388 dose, pooled placebo, time since last dose (days:hrs:min), resolution date and time and maximum intensity based on Table 8 of the protocol for severity assessments. Additionally, data listings will be provided.

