5. STUDY OBJECTIVES AND ENDPOINTS

Objectives	Endpoints
Primary	
 To determine the safety and tolerability profile of CD388 Injection when dosed either by intramuscular (IM) or subcutaneous (SQ) administration as a single dose to healthy adult subjects. Incidence and severity of treatment-emergent adverse events (TEAEs), including but not limited to adverse events (AEs) and serious adverse events (SAEs) (including systemic reactogenicity/injection site reactions and hypersensitivity reactions), AEs leading to study drug discontinuation and/or study withdrawal, vital signs, 12-lead electrocardiograms (ECGs), and clinical laboratory tests (including hematology, coagulation, serum chemistry, and urinalysis), after a single dose of CD388.
Secondary	
 To determine the plasma pharmacokinetic (PK) profile of CD388 Injection when dosed either by IM or SQ administration following a single dose and a repeated single dose to healthy adult subjects. Pharmacokinetic parameters following CD388 Injection administration: maximum plasma concentration (C_{max}), time to maximum plasma concentration (T_{max}), terminal elimination half-life ($t_{1/2}$), apparent clearance (CL/F), apparent volume of distribution (V_z/F), area under the plasma concentration-time curve from time 0 to time of last quantifiable sample (AUC_{0-t}), area under the plasma concentration-time curve from time 0 extrapolated to infinity ($AUC_{0-\infty}$). Incidence and severity of TEAEs, including but not limited to AEs and SAEs (including systemic reactogenicity/injection site reactions and hypersensitivity reactions), AEs leading to study drug discontinuation and/or study withdrawal, vital signs, ECGs, and clinical laboratory tests (including hematology, coagulation, serum chemistry, and urinalysis) after a repeated single dose of CD388.

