12. STATISTICAL METHODS

A Statistical Analysis Plan (SAP) will be prepared and finalized before unblinding for the first interim analysis. Any deviations from the final SAP will be described and justified in the study report. All statistical analyses will be performed using SAS®.

Descriptive statistics, including the numbers and percentages for categorical variables, and the numbers, means, standard deviations, medians, minimums, and maximums for continuous variables, will be provided. All data will be summarized separately by dose level, route (IM or SQ), and study drug (CD388 Injection or placebo). Listings of individual subject data will also be produced.

Safety, PK, and pharmacodynamics will be summarized using descriptive statistics. There will be no formal hypothesis testing.

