12.7. Determination of Study Sample Size

Up to 77 subjects will be enrolled in this study, with approximately 56 of these subjects expected to receive CD388 Injection. The number of subjects was selected to allow sufficient evaluation of safety and tolerability, and PK, and is consistent with standards of practice for first-in-human (FIH) studies.

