3 STUDY DESIGN

3.1 General Description

This is a first-in-human (FIH), Phase 1, single-center, prospective, randomized, double-blind study of ascending single doses of CD388 Injection administered IM or SQ to healthy adult subjects followed by another single dose of CD388 Injection administered by the same route 3 months or 5 effective half-lives, whichever is longer, after the first dose in the middle and high dose groups (dosing may be adjusted for tolerability). The goals are to assess safety, tolerability, immunogenicity (anti-drug antibodies [ADA]), and PK of CD388.

Dose levels of CD388 to be assessed will follow an ascending single dose design with the starting dose based on findings from 3-month rat and monkey toxicology studies. Within each route (IM and SQ dose, route assignment is unblinded), subjects will be randomized to receive a single dose of CD388 Injection or saline placebo (treatment assignment is blinded) according to the design. It should be noted that each cohort will be divided into 2 groups identified as “sentinel” groups (randomized 1:1) and “main” groups (randomized 7:2):

- Low dose level: Cohort 1A (IM) and Cohort 1B (SQ) – each route n = 2 sentinel and n = 9 main
- Mid dose level: Cohort 2A (IM) and Cohort 2B (SQ) – each route n = 2 sentinel and n = 9 main
- High dose level: Cohort 3A (IM) and Cohort 3B (SQ) – each route n = 2 sentinel and n = 9 main
- Highest dose level: Cohort 4B (SQ) – n = 2 sentinel and n = 9 main

For each route, the sentinel or first group of 2 subjects (1 CD388: 1 placebo) at a dose level will be administered blinded study drug and closely monitored for safety for at least 1 week. If no drug-related SAEs or drug-related Grade ≥ 3 AEs have occurred, the subjects in the corresponding main group may be dosed within 24 hours. The observation duration may be adjusted for the sentinel groups in Cohorts 2A, 2B, 3A, 3B, and 4B based on data from previous cohorts.

Subjects in Cohort 4B will receive a single dose of CD388 or placebo. Subjects in Cohorts 2A and 2B and Cohorts 3A and 3B will receive a second single dose of CD388 Injection or placebo after washout of 3 months or 5 effective half-lives, whichever is longer, after the first dose if it is determined that the safety and tolerability of the first dose is acceptable upon review of the cumulative safety data.

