8 SAFETY ANALYSIS

Unless otherwise specified, all available data will be listed and summary tables for safety assessments will be presented by injection route (IM or SQ), CD388 dose, and pooled placebo for the safety population as detailed in [Table 6](#).

Continuous variables will be summarized (absolute values and change from baseline) using descriptive statistics. The TEAEs occurring after the first single dose and after the second single dose will be analyzed separately.

Table 6: Data Presentations for Safety Assessment

Data	Variables	Presentation
Adverse events	Adverse event, description, date and time, severity, relationship to study drug, action taken with study drug, whether the AE caused the subject to discontinue from the study, study days, and outcome, Duration of AE, Date and time of onset, date, and time of resolution.	
Listings:
 
• Reported AEs,• Serious Adverse Event (SAE) 
Summary Tables, including number and percentage of subjects experiencing:
 
• Treatment-emergent adverse events (TEAEs),• TEAEs related to study drug• TEAEs by severity,• Serious TEAEs,• Influenza-like TEAEs (reported during the outpatient follow-up period),• Adverse Events of Special Interest (AESIs),• TEAEs leading to study withdrawal• TEAEs leading to study drug withdrawal (cohorts 2a, 2b, 3a, 3b)• Overall summary will include:
○ At Least One TEAE○ At Least One Drug-Related TEAE○ Maximum Severity:
➢ Mild,➢ Moderate➢ Severe➢ Life-threatening➢ Death○ At Least One SAE○ At Least One Drug-Related SAE○ Death○ AE leading to study drug withdrawal (Pooling placebo from cohorts 2a, 2b, 3a, 3b)○ AE leading to study withdrawal
Concomitant medications	All medications taken during the study (as defined in the protocol and including prior medications that are continued), dose, units, route, indication/ reason taken, and date and time.	
Listing
 
• Note: includes coded terms (anatomic therapeutic chemical [ATC] level 4 and preferred name)

Data	Variables	Presentation																
Extent of exposure	Study drug administration dose, Route, units, date, time, Cohort	
Listing
																

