	CD388 50 mg (N = XX)	CD388 150 mg (N = XX)	CD388 450 mg (N = XX)	Pooled Placebo	CD388 50 mg (N = XX)	CD388 150 mg (N = XX)	CD388 450 mg (N = XX)	mg (N = XX)	CD388 900	ETC. (N = XX)	Chang e from Observe erved ed Base line	Chang e from Observe erved ed Base line	Chang e from Observe erved ed Base line	Chang e from Observe erved ed Base line	Change from Baseline	

Date: VERSION - YYYY-MM-DD Data Source: xxx Program Source: xxx.sas

IM = Intramuscular; SQ = Subcutaneous; SD = Standard Deviation.

[1] Note: Baseline is the measurement of the last predose measurement was used.

<Laboratory Panel> = Hematology; Chemistry; Urinalysis; Coagulation; Lipid;

<Programming Note>

It can be presented separately (i.e., IM one page and SQ another).

ETC.= for SQ: Cohort 4B CD388 - Pooled Placebo

Table 14.2.20 Template T4.2: Summary of Potentially Clinically Significant (PCS) Values <Laboratory Panel> (Safety Population)

Table 14.3.2.6

Number (Percentage) of Subjects with Potentially Clinically Significant (PCS) Values in Hematology at Any Post-baseline Visit Safety Population

Visit	Parameter	PCS Criteria	IM Route						SQ Route						IM Route						CD388 900	mg (N = XX)	ETC. (N = XX)			
			CD388 50			CD388 150			CD388 450			Pooled Placebo			CD388 50			CD388 150			CD388 450			CD388 900	mg (N = XX)	ETC. (N = XX)
			n/m	(%)	n/m	(%)	n/m	(%)	n/m	(%)	n/m	(%)	n/m	(%)	n/m	(%)	n/m	(%)	n/m	(%)	n/m	(%)	n/m	(%)		
	Albumin		x/xx (xx..x)		x/xx (xx..x)		x/xx (xx..x)		x/xx (xx..x)		x/xx (xx..x)		x/xx (xx..x)		x/xx (xx..x)		x/xx (xx..x)		x/xx (xx..x)		x/xx (xx..x)		x/xx (xx..x)			
			x/xx (xx..x)		x/xx (xx..x)		x/xx (xx..x)		x/xx (xx..x)		x/xx (xx..x)		x/xx (xx..x)		x/xx (xx..x)		x/xx (xx..x)		x/xx (xx..x)		x/xx (xx..x)		x/xx (xx..x)			
			x/xx (xx..x)		x/xx (xx..x)		x/xx (xx..x)		x/xx (xx..x)		x/xx (xx..x)		x/xx (xx..x)		x/xx (xx..x)		x/xx (xx..x)		x/xx (xx..x)		x/xx (xx..x)		x/xx (xx..x)			
	Alanine aminotransfer ase (F)		x/xx (xx..x)		x/xx (xx..x)		x/xx (xx..x)		x/xx (xx..x)		x/xx (xx..x)		x/xx (xx..x)		x/xx (xx..x)		x/xx (xx..x)		x/xx (xx..x)		x/xx (xx..x)		x/xx (xx..x)			
	Alanine aminotransfer ase (M)		x/xx (xx..x)		x/xx (xx..x)		x/xx (xx..x)		x/xx (xx..x)		x/xx (xx..x)		x/xx (xx..x)		x/xx (xx..x)		x/xx (xx..x)		x/xx (xx..x)		x/xx (xx..x)		x/xx (xx..x)			
	...																									
Pre-Dose	Albumin		x/xx (xx..x)		x/xx (xx..x)		x/xx (xx..x)		x/xx (xx..x)		x/xx (xx..x)		x/xx (xx..x)		x/xx (xx..x)		x/xx (xx..x)		x/xx (xx..x)		x/xx (xx..x)		x/xx (xx..x)			

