Day xx	Increases from Baseline	n	xx	xx	xx	xx	xx	xx	xx	xx	
		> 30 msec and	xx	xx	xx (xx..x)	xx	xx (xx..x)	xx	xx (xx..x)	xx (xx..x)	
		≤ 60 msec	(xx..x)	(xx..x)		(xx..x)		(xx..x)			
		> 60 msec	xx	xx	xx (xx..x)	xx	xx (xx..x)	xx	xx (xx..x)	xx (xx..x)	
			(xx..x)	(xx..x)		(xx..x)		(xx..x)			
Day xx	Absolute Values	n	xx	xx	xx	xx	xx	xx	xx	xx	
		> 450 msec and	xx	xx	xx (xx..x)	xx	xx (xx..x)	xx	xx (xx..x)	xx (xx..x)	
		≤ 480 msec	(xx..x)	(xx..x)		(xx..x)		(xx..x)			
		> 450 msec and	xx	xx	xx (xx..x)	xx	xx (xx..x)	xx	xx (xx..x)	xx (xx..x)	
		≤ 500 msec	(xx..x)	(xx..x)		(xx..x)		(xx..x)			
		> 500 msec	xx	xx	xx (xx..x)	xx	xx (xx..x)	xx	xx (xx..x)	xx (xx..x)	
			(xx..x)	(xx..x)		(xx..x)		(xx..x)			
Day xx	Increases from Baseline	n	xx	xx	xx	xx	xx	xx	xx	xx	
		> 30 msec and	xx	xx	xx (xx..x)	xx	xx (xx..x)	xx	xx (xx..x)	xx (xx..x)	
		≤ 60 msec	(xx..x)	(xx..x)		(xx..x)		(xx..x)			
		> 60 msec	xx	xx	xx (xx..x)	xx	xx (xx..x)	xx	xx (xx..x)	xx (xx..x)	
			(xx..x)	(xx..x)		(xx..x)		(xx..x)			
...											

Date: VERSION - YYYY-MM-DD

Data Source: xxx

Program Source: xxx.sas

IM = Intramuscular; SQ = Subcutaneous; SD = Standard Deviation.

Note: Baseline is the measurement of the last predose measurement was used.

<Programming Note>

ETC.= for SQ: Cohort 4B CD388 - Pooled Placebo
It can be presented separately (i.e., IM one page and SQ another).

Table 14.2.26 Template T5.4: Reactogenicity/Injection Site Inspection (Safety Population)

Table 14.3.5.1
 Summary of Reactogenicity/Injection Site Inspection
 (Safety Population)

	IM Route								SQ Route	
	CD388	CD388	CD388	Pooled	CD388	CD388	CD388	CD388	ETC.	
50 mg	150 mg	450 mg	Placebo	50 mg	150 mg	450 mg	900 mg			
(N = XX)	(N = XX)	(N = XX)	(N = XX)	(N = XX)	(N = XX)	(N = XX)	(N = XX)			
Subject With at Least One Injection Site Reaction [n(%)]	Xx (xx.x)		Xx (xx.x)							
Injection Site XX Grade 1	Xx (xx.x)		Xx (xx.x)							

Date: VERSION - YYYY-MM-DD

Data Source: xxx

Program Source: xxxx.sas

IM = Intramuscular; SQ = Subcutaneous.

Note: Baseline is the measurement of the last predose measurement was used.

<Programming Note>

ETC.= for SQ: Cohort 4B CD388 - Pooled Placebo

It can be presented separately (i.e., IM one page and SQ another).

[figure not shown]

FIGURE MOCK SHELLS

The templates indicate the content that will be presented in the figures. The appearance, e.g., the actual time points or values, the layout of the figure, fonts, or other typographic detail, may be different in the final versions of the figures.

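### The injection-site reaction table and the ever-abnormal laboratory and vital-sign rows are not split by first and second dose, so columns with one and two injections are set side by side

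*SAP*

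**What the plan says.** SAP 3.1 provides that "Subjects in Cohorts 2A and 2B and Cohorts 3A and 3B will receive a second single dose of CD388 Injection or placebo". The protocol synopsis gives Cohorts 1A, 1B and 4B a single dose. Protocol section 5 makes safety after one dose the primary objective ("To determine the safety and tolerability profile of CD388 Injection when dosed either by intramuscular (IM) or subcutaneous (SQ) administration as a single dose") and lists safety after a repeated dose as a separate secondary endpoint. Both endpoints name injection-site reactions, vital signs and laboratory tests.

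For adverse events the SAP respects this separation: "The TEAEs occurring after the first single dose and after the second single dose will be analyzed separately". The TEAE shells, 14.3.1.1 to 14.3.1.14, come in first-dose and second-dose pairs.

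Three other safety displays do not:

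- **Injection-site reactions.** SAP 8.6 reads: "Reactogenicity/Injection Site Inspection will be summarized descriptively, by injection route (IM or SQ), CD388 dose, pooled placebo, time since last dose". Resolution and maximum intensity follow. The counting row of shell 14.3.5.1 begins "Subject With at Least One Injection Site Reaction [n".
- **Laboratory PCS values.** Shell 14.3.2.6, the template for all panels, is titled "Number (Percentage) of Subjects with Potentially Clinically Significant (PCS) Values in Hematology at Any Post-baseline Visit".
- **Vital-sign PCS values.** Shell 14.3.3.2 opens with a block counting subjects with one or more PCS values after baseline.

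None of the three has a second-dose companion.

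**The concern.** A count of subjects who ever had an event grows with the number of opportunities to have one. In these displays that number depends on the dose column. Subjects on 150 and 450 mg have two injections and two rounds of site inspection (Days 1, 2 and 3–6 in each period). Subjects on 50 and 900 mg have one of each. Grouping by time since last dose does not help, because it does not say which dose was the last.

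The placebo column is a blend of one- and two-injection subjects that no active column shares, so it is not a like-for-like comparator for any of them. For 150 mg, 450 mg and placebo, the ever-count matches neither the single-dose primary endpoint nor the repeat-dose secondary endpoint. In the SQ arm the artefact would look like a rise and then a fall at 900 mg. In the IM arm it would look like a step up after 50 mg. Either could be misread in a first-in-human dose comparison.

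**Working it through.** **1. Reproduce the planned numbers.** Each of 7 cohorts has 8 CD388 and 3 placebo subjects (SAP Table 2). IM: 3×8 = 24 and 3×3 = 9. SQ: 4×8 = 32 and 4×3 = 12. The total is 77, of whom 24 + 32 = 56 receive CD388. This agrees with protocol 12.7: "Up to 77 subjects will be enrolled in this study, with approximately 56 of these subjects expected to receive CD388 Injection".

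**2. Injections per column.**

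- 50 mg (1A, 1B) and 900 mg (4B): one.
- 150 mg (2A, 2B) and 450 mg (3A, 3B): two.
- IM placebo: 3 subjects with one (1A) and 6 with two (2A, 3A). The mean is (3×1 + 6×2)/9 = 1.67.
- SQ placebo: 6 with one (1B, 4B) and 6 with two (2B, 3B). The mean is (6×1 + 6×2)/12 = 1.50.

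**3. Expected ever-reaction rate with no drug or dose effect.** Let p be the risk per injection, the same for drug and saline, and ρ the within-subject correlation between injections. Neither is in the documents. I assume p from 5% to 30% and ρ from 0 to 1.

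- One injection: p.
- Two injections: q = 1 − [(1−p)² + ρp(1−p)].
- IM placebo: (3p + 6q)/9. SQ placebo: (6p + 6q)/12.

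At p = 10% and ρ = 0, q = 1 − 0.81 = 19%. IM placebo is (0.30 + 1.14)/9 = 16%, and SQ placebo is (0.60 + 1.14)/12 = 14.5%.

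| ρ | p: 50 and 900 mg | q: 150 and 450 mg | IM placebo | SQ placebo | Extra reactors per 8, 8(q−p) |
|---|---|---|---|---|---|
| 0 | 5% | 9.75% | 8.2% | 7.4% | 0.38 |
| 0 | 10% | 19.0% | 16.0% | 14.5% | 0.72 |
| 0 | 20% | 36.0% | 30.7% | 28.0% | 1.28 |
| 0 | 30% | 51.0% | 44.0% | 40.5% | 1.68 |
| 0.5 | 10% | 14.5% | 13.0% | 12.25% | 0.36 |
| 0.5 | 30% | 40.5% | 37.0% | 35.25% | 0.84 |
| 1 | any p | p | p | p | 0 |

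The 900 mg column exists for SQ only. At p = 10% and ρ = 0, 50 mg IM looks 6.0 points better than its placebo and 150/450 mg IM looks 3.0 points worse. In SQ the gaps are 4.5 points each way.

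**4. How often this would be visible.** Take two columns of 8 with p = 10% and ρ = 0. The 150 mg count exceeds the 50 mg count with probability 56%, and the reverse has probability 18%. If each table holds one injection per subject, the chance is 32% each way.

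**5. Laboratory PCS opportunities.** Counting post-dose laboratory visits in the schedules gives 10 for 50 mg, 11 for 900 mg and 20 for 150/450 mg (21 if the second-period Day −1 sample is included). I attach no rate. Repeated laboratory values in one subject are not independent draws, and the documents give no per-visit frequency.

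**6. Second-dose baseline.** SAP 10.3 takes the second-dose baseline from the predose time point on the dosing date. The second-period schedule (protocol Table 2, SAP Appendix B) draws laboratory samples on Day −1 and none on Day 1. A second-dose laboratory PCS table would therefore have no baseline under the current rule, and the shell's denominator requires a non-PCS baseline.

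**The case against.** The case against is substantial, and part of it stands.

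- **Site reactions also reach the dose-split tables.** Protocol 9.8 requires abnormal inspection findings to be reported as adverse events. They therefore enter the paired TEAE tables, and the reactogenicity listing gives onset and time since last dose. This stands as mitigation. But those tables use MedDRA terms. The summary promised in protocol 12.3 (any local reaction; pain, tenderness, erythema and induration; severity of each) is planned only in the unsplit table.
- **PCS values are also tabulated by time point.** SAP Table 6 plans this, and the shells carry such blocks. A by-visit row does not grow with the number of visits. However, Days 2, 7, 14, 21 and 30 occur in both periods, and the shells have no period label.
- **The trial is descriptive:** "There will be no formal hypothesis testing". True, so no error rate is affected. A descriptive comparison still needs comparable columns.

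Three stronger readings are tempting, and the documents do not support them. One is that the SAP separates doses for TEAEs alone. It also does so for PK outputs, the dosing listings, study days (10.1) and baseline (10.3). Another is that safety after a single dose would go unreported. The first-dose TEAE tables cover it, site reactions included. The third is that a false dose pattern is bound to appear. Under the assumptions least favourable to the plan (ρ = 0), the full SQ pattern, with 150 and 450 mg both above 50 mg and 900 mg below placebo, has probability about 22% at p = 10% and 33% at p = 20%. The 900 mg column would look worse than placebo in 33% and 29% of trials respectively.

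**Conclusion.** The point holds as a gap in the SAP text and shells that biases three safety summaries in expectation. It rests on the design (one versus two injections by cohort) and on the absence of a dose-number split, both plain in the documents. Its size rests on assumed quantities: equal risk per injection, a value for that risk, and the within-subject correlation. At 10% risk the expected excess in a two-injection column of 8 is 0.72 subject with independence, 0.36 at correlation 0.5, and nil at correlation 1.

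The dose-split TEAE tables and the by-visit PCS rows limit the damage without removing it. Since the SAP splits by dose in most other places, the gap looks like an omission and not a deliberate choice. It should be corrected, but it does not threaten the trial's ability to report safety.

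**What to change.** In SAP 8.2, 8.3 and 8.6, and in shells 14.3.2.6 (all panels), 14.3.3.2 and 14.3.5.1, adopt the split already used for TEAEs:

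- **First-dose tables:** all cohorts, data after injection 1 and before injection 2, with pooled placebo of 9 (IM) and 12 (SQ).
- **Second-dose tables:** Cohorts 2A, 2B, 3A and 3B only, with the placebo subjects who received the second dose, up to 6 per route.
- **By-visit PCS rows:** label each by dosing period.
- **SAP 10.3:** define the second-dose baseline as the last non-missing value before the second dose, so that the Day −1 laboratory sample counts.

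Each table then holds one injection per subject, and the no-effect expectation for site reactions is p in every column. The cost is SAP and shell wording and a few extra table runs, with no new data. The second-dose columns will be small. Some difference in PCS follow-up length remains, for example about Day 120 for 50 mg against Day 206 for 900 mg, and a footnote should say so.
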